7.2. Prior and Concomitant Medications

Prior and concomitant medications, including antidiabetic medications, will be coded using the latest WHO Drug dictionary Version June, 2010 or higher and classified into the default anatomical therapeutic chemical (ATC) classification system codes provided by the system (the first ATC code by alphabetic order).

Any medication that was stopped prior to the treatment start date will be considered a prior medication. Medication taken at any time between the treatment start date and the date of last contact, inclusive, will be considered concomitant medication. If the medication start or stop dates are missing or partially

missing and the medication is not checked as ongoing, general imputation rules from [section 4.5](#) will be applied. Subject data including prior and concomitant medications including antidiabetic medications will be presented.

7.2.1. Concomitant Statin Therapy

The high potency statin therapy administered to the study participants will be summarized on FAS including the type of statin (Atorvastatin or Rosuvastatin) and doses. Dose adjustments (increase or decrease dose after first dose administered) will be summarized in a manner similar to study drug dose reduction.

8. Efficacy Analysis

All efficacy analyses will use the FAS set. Subjects will be analyzed according to randomized treatment group. Key efficacy analyses will also be performed on the PPS as supportive evidence and to assess the robustness of the efficacy findings. Each table presents the population that the analysis was conducted on.

Time to event analyses for primary and secondary endpoints will use the Kaplan-Meier method to estimate the median survival time and its 2-sided 95% confidence intervals (CIs). A stratified log rank test will be used for calculating the 2-sided p-value for treatment comparisons.

Primary and key secondary endpoint analyses will include presentation of estimated hazard ratios and associated 2-sided CI obtained from a stratified Cox Proportional Hazards (CPH) model. Assessment of proportional hazards assumption for treatment will be assessed through diagnostic checks involving plots of Schoenfeld residuals obtained from CPH model that fit the primary endpoint of narrowly defined MACE.

For the primary, secondary, and exploratory endpoints, time to event will be the time from the date of randomization to the date of first occurrence of any event in the respective endpoint. A subject who did not have an episode of an event for a given endpoint throughout the study, will be censored for that endpoint at the day of last contact. For any interim database cut, a subject who has not discontinued from the study and did not have an episode of an event for a given endpoint will be censored for that endpoint at the date of the interim cutoff.

Statistical tests for comparing RVX000222 arm with Placebo will be conducted for the primary endpoint and other efficacy endpoints described in [Section 3.2](#). The key secondary endpoints will be tested for superiority in order only if superiority is established for primary efficacy endpoint. The key secondary endpoints will be tested sequentially following a pre-specified order as seen in [Section 3.2.2](#).

The multiplicity of the analyses of the primary and key secondary endpoints will be adjusted using a Sequential Gate-Keeping Procedure. This procedure will preserve the Family Wise Error Rate in light of multiple analyses being performed. The analyses will be performed in sequence until one of the analyses has failed to show the significance level of $p = 0.05$. That is, in order to preserve the overall alpha level at 0.05 across the narrowly defined MACE and broadly defined MACE endpoints, formal statistical inference for the broadly defined MACE can only be made if superiority of RVX222 is demonstrated for the primary efficacy endpoint, narrowly defined MACE, at the two-sided 0.05 significance level.

For continuous endpoints pertaining to liver function, lipid profile, kidney function, HbA1c, fasting glucose, and insulin, descriptive statistics (N , mean, median, standard deviation, quartiles, minimum and maximum) will be provided by treatment group at specified visits.

Quantitative endpoints that are defined as a (percent) change from baseline will be analyzed using analysis of covariance (ANCOVA) models with treatment group as a factor and the baseline value as a covariate. Mixed-effect model repeated measurements (MMRM) will be used to analyse a subset of secondary outcomes over time.

Subjects will continue to be followed for both primary and secondary endpoints until 250 adjudicated primary endpoints have been observed. Other than the pre-specified sequential testing, no additional alpha adjustments for multiplicity will be made. That is, no multiplicity adjustment is planned for testing regarding the other secondary and exploratory endpoints as these endpoints are considered supportive.

8.1. Adjudication Process of the Key Endpoints

Potential CV events will be identified by comparing all SAE preferred terms to a pre-established list of MedDRA preferred terms. The terms included in the pre-established list are designed to broadly capture

potential CV events from MedDRA SMQs, system organ classes, preferred terms, and lower-level terms specified in the FDA draft guidance document “Endpoints and Standardized Data Collection for Cardiovascular Outcomes Trials”, issued July 22, 2009. All reported terms that code to a listed preferred term will be forwarded to the Clinical Events Committee (CEC) for adjudication. The details of CEC operations and the clinical definitions of the CV outcomes are specified in the CEC charter (v3.0 / 08JUN2017).

High level results of the CEC adjudication of potential CV events as entered into PPD PVG EAS (Electronic Adjudication System) will be transferred and maintained in a SAS dataset. All potential CV events and corresponding adjudication outcomes will be summarized. In addition, association of these events with respect to the primary and key secondary endpoints will be flagged for the analyses. The *possible* adjudication outcomes are categorized as follows:

- Deaths
 - Cardiovascular deaths (including coronary heart disease (CHD) deaths)
 - Non cardiovascular deaths
 - Undetermined cause of death
- Non-fatal cardiovascular events
 - Acute myocardial infarction
 - Hospitalization for unstable angina and evidence of new or progressive obstructive coronary disease.
 - Hospitalization for other angina
 - Hospitalization for heart failure
 - Non- Elective (Urgent/Emergency/Salvage) Coronary Revascularization
 - Stroke

8.2. Primary Analysis

The primary analysis will be a time-to-event analysis. The distributions of the primary endpoint within the RVX000222 and placebo groups will be compared using a two-sided stratified log-rank test (LRT) with an $\alpha = 0.05$ level of significance (two sided). Time to first narrowly defined MACE, defined as a single composite endpoint of CV Death or Non-fatal MI or Stroke, will be calculated using randomization date and date of the confirmed event, or date of last contact for censored subjects. For the purpose of the primary analysis and all subsequent analyses involving CV deaths, events within the undetermined cause of death category will be considered CV deaths. All subjects will be followed until drop-out, death, or study closure. Drop-out may be due to withdrawal of consent from further data collection or lost to follow-up. Subjects who drop-out or are alive at study closure will have their event times censored at the time of last contact.

The primary efficacy analysis will be performed on the FAS. The number and percentage of subjects who experienced the narrowly defined MACE, median survival time and corresponding 95% confidence intervals (CIs) will be tabulated and presented by treatment group. A stratified log-rank test and corresponding test statistic, stratifying by country of enrollment and prescribed statin therapy (atorvastatin or rosuvastatin), at a two-sided α level of 0.05, will be used to compare the survival rate between the two treatment groups. If stratifying by country results in too many empty cells, stratifying by geographic region may be considered.

As supportive analyses, the primary efficacy analysis will be

1. repeated for the PPS set
2. repeated for FAS set but using just events adjudicated as CV deaths excluding “undetermined cause of death events”. This analysis will be outside the analysis hierarchy of the study and will not influence secondary endpoint analyses.
3. performed on the FAS using an unstratified LRT as a supportive analysis.

Kaplan-Meier plots for the primary and key secondary endpoints by treatment groups will be presented. Presentation of primary analyses will include estimated hazard ratios and associated 2-sided CI obtained from Cox Proportional Hazard (CPH) models with treatment as the single factor, stratified by country of enrollment and prescribed statin therapy (atorvastatin or rosuvastatin).

Subgroup analyses will be conducted for the primary endpoint based on the following categorizations:

- Subjects receiving rosuvastatin and those receiving atorvastatin
- Index acute coronary syndrome ≤ 30 days and > 30 days pre randomization
- LDL/HDL/TG’s above and below median value for the study sample
- HbA1c above and below median value for the study sample
- GFR ≥ 60 mL/min and < 60 mL/min as calculated at baseline
- hs-CRP \geq and below the median, as collected at Visit 2
- ALP above and below median as collected at screening,
- Males and Females

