4.0 STUDY DESIGN

This is a double-blind, placebo-controlled, 2-arm parallel-group (allocation ratio 1:1), study of RVX000222 at a daily dose of 100 mg b.i.d. (total daily dose of 200 mg) or matching placebo in combination with high intensity statin therapy administered to T2DM subjects with history of recent CAD event and HDL-C level $<$ 40 mg/dL in males or $<$ 45 mg/dL in females.

After an initial screening period of 1 to 2 weeks during which subjects will demonstrate tolerance of high intensity statin therapy, subjects will be randomized to either RVX000222 100 mg b.i.d. or matching placebo with continued statin treatment. This combination treatment period will continue until 250 narrowly defined MACE events have occurred in the study and all surviving patients have been followed for at least 24 weeks from randomization. Blinded treatment with RVX000222 or matching placebo will then be discontinued. Subjects will remain on high intensity statin therapy for 4 more weeks until the Follow-Up Visit.

The study is an event-based trial and will continue until 250 primary endpoint events have occurred. Study treatment will be terminated after the 250th adjudicated event occurs. At that time, all subjects actively treated will conduct their Last Visit on Treatment and then be discontinued from investigational drug. Subjects will then return 4 weeks after last day of treatment for the Follow-Up Visit.

A Clinical Steering Committee (CSC) will oversee the conduct of the study. A Data Safety Monitoring Board (DSMB) will oversee the safety data for this study and independent CEC will adjudicate all suspected MACE composite events in an ongoing manner. An independent team (including an independent statistician) will perform the prospective unblinded analyses described in Section 10.8 (Data Safety Monitoring Board) and will report the results to the DSMB. Each committee will develop a charter to describe their activities and responsibilities prior to initiation of the study.

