3.7. Study Visits

After randomization to RVX000222 or placebo, visits will occur every 2 weeks until Week 12. From Week 12 to Week 28, visits will occur every 4 weeks. From Week 28 until the Last Visit on Treatment, visits will occur approximately every 12 weeks. Four weeks after the Last Visit on Treatment, subjects will return for a final Follow-Up Visit. The Schedule of Events can be found in the study protocol. Study treatment will be terminated in all currently participating subjects when it is estimated that 250 subjects have experienced a narrowly defined MACE event. At that time, all subjects actively treated will conduct their Last Visit on Treatment as soon after as possible while ensuring at least 6 months of study therapy and then return 4 weeks after last day of treatment for the Follow-Up Visit. Procedures are defined in the Schedule of Events.

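### Does an undefined study closure leave it open which events enter the primary analysis?

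*SAP*

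**What the plan says.** **Follow-up and censoring.** SAP 8.2: "All subjects will be followed until drop-out, death, or study closure". It continues: "Subjects who drop-out or are alive at study closure will have their event times censored at the time of last contact". SAP 8 gives the same rule for every time-to-event endpoint: a subject with no event throughout the study "will be censored for that endpoint at the day of last contact". A calendar cut-off appears only for interim database cuts, where such a subject "will be censored for that endpoint at the date of the interim cutoff".

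**Event count.** Protocol 4.0: "Study treatment will be terminated after the 250th adjudicated event occurs". SAP 3.7 ends treatment "when it is estimated that 250 subjects have experienced a narrowly defined MACE event". SAP 8 adds: "Subjects will continue to be followed for both primary and secondary endpoints until 250 adjudicated primary endpoints have been observed". Protocol 9.6.1 says much the same without the word adjudicated. The synopsis (Primary Analysis) places the primary analysis after the 250th adjudication-confirmed event.

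**Off-drug period.** Most places put the Follow-Up Visit 4 weeks after the Last Visit on Treatment. The protocol synopsis (Study Procedures) gives 4 to 16 weeks in one sentence and 4 weeks a few lines later.

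**Deaths.** SAP 5.1 plans a final vital-status check for subjects who leave early. For cause of death, SAP 8.2 states that "events within the undetermined cause of death category will be considered CV deaths".

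**The concern.** Study closure ends follow-up in the primary analysis, and it has no date and no definition. Two programmers could build different primary datasets. One would count every adjudicated event up to the Follow-Up Visit; the other would stop at the 250th, relying on the sentence in SAP 8 that follows subjects until 250 adjudicated endpoints. Events in the off-drug weeks might dilute the treatment effect. If treatment were stopped on an estimate, the confirmed count might fall short of the 250 on which the power rests. A death found only by a records check might or might not become a primary event. The primary test is the gate to all key secondary endpoints, so a cut-off chosen after unblinding would be open to challenge.

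**Working it through.** **1. What the text implies about off-drug events**

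- The endpoint (Protocol 3.1, SAP 3.2.1) runs from randomization to the first confirmed event, with no on-treatment limit.
- Event-free subjects are censored at last contact (SAP 8, 8.2), and participation ends on that day (SAP 7.1.1).
- The follow-up period is part of total participation (synopsis, Length of Study), and Protocol 6.6 treats the Follow-Up Visit as the final study visit.
- SAEs are collected for the duration of the study (Protocol 8.2.3.3), and potential MACE are reported as SAEs and adjudicated (8.2.3.5).

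Taken literally, adjudicated events up to the Follow-Up Visit count. The sentences that follow subjects until 250 events (Protocol 9.6.1, SAP 8) sit in the multiplicity text and can be read as a minimum. That fits Protocol 4.0 and SAP 4.5, which also require 24 weeks of follow-up for all survivors and so allow the count to pass 250.

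**2. The trigger**

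SAP 3.7 and Protocol 4.0 both govern the end of treatment; neither is written as a definition of study closure. SAP 3.7 belongs to a section that describes itself as restating protocol features for context. Whichever wording governs treatment, the primary analysis needs 250 adjudication-confirmed events. A primary analysis with fewer confirmed events would depart from the plan.

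**3. Reproducing the plan's figure**

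Inputs (SAP 4.2): HR 0.7, two-sided 5%, 250 events, 10.5% placebo events at 18 months, accrual 1.7 years, total 2.75 years, 5% drop-out by year one, 2,400 subjects split 1:1.

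- Placebo hazard: −ln(0.895)/1.5 = 0.0740 per year. Active: 0.7 × 0.0740 = 0.0518, which gives the stated 7.47% at 18 months. Drop-out hazard: −ln(0.95) = 0.0513.
- Power = Φ(√d/2 × |ln HR| − 1.96). At d = 250: Φ(7.906 × 0.3567 − 1.96) = Φ(0.860) = 80.5%.
- Expected events by 2.75 years: 149.0 + 106.6 = 255.6, so 2,400 subjects do yield 250.

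**4. Size of the four-week window**

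- Event 250 is expected at 2.704 years (week 141). Still at risk: 953 + 993 = 1,946, from (1,200/1.7) ∫ exp[−(λ+δ)(T−a)] da over entry times a from 0 to 1.7, in each arm.
- Effect persists: 953 × 0.0740 × 4/52.18 + 993 × 0.0518 × 4/52.18 ≈ 5.4 + 3.9 = 9.3 events. Power at d = 259.3 is 81.9%.
- Effect stops, both arms at the placebo hazard: about 11.0 events. Average log HR = (250/261) × ln 0.7, so HR 0.711 and power 78.8%. With both arms at the average hazard (9.3 events) power is 79.1%.

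If every subject returned at 16 weeks, the window would hold 37 to 44 events, with power of about 74% (effect stops) to 86% (persists).

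**5. Vital-status deaths**

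- By week 141, 2,400 − 1,946 = 454 subjects have left the risk set: 250 with events and 204 by drop-out. Time from drop-out to 2.704 years totals 209.5 person-years.
- Assume deaths at 20–50% of the mean primary-event hazard, (0.0740 + 0.0518)/2 = 0.0629. Then 209.5 × 0.0629 × 0.2 = 2.6, and × 0.5 = 6.6 deaths.
- With no effect after drop-out, log HR = 250/(250 + deaths) × ln 0.7: HR 0.703 to 0.706, power 80.1% to 79.5%.

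**The case for a change.** The best case for acting is that the last-contact rule and the sentence following subjects until 250 adjudicated endpoints point different ways. The choice feeds the one test that gates the key secondary endpoints, and a few lines before unblinding would cost nothing. The absence of a definition is real. The estimated and adjudicated wordings do disagree, as do the two follow-up intervals in the synopsis; those passages must be reconciled, and I take no side on the schedule or on the rule for stopping treatment.

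Less stands on the analysis itself. The censoring rule is written twice, and it is applied without regard to arm or to early drug discontinuation: subjects off drug stay in the study (SAP 3.4) and are analysed as randomized (SAP 4.4.1). The 16-week range needs one sentence of the synopsis to prevail and every subject to return at its limit.

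On vital status, Protocol 6.10.3 lists such checks as a form of continued participation, separate from full withdrawal. All deaths are adjudicated (Protocol 8.2.3.5), and SAP 8.2 already plans a supportive analysis without undetermined deaths. A question remains for subjects lost to follow-up, but it concerns a handful of deaths. A rule that counted deaths found later while leaving survivors censored at their earlier last contact would be worse than silence, because follow-up would then depend on outcome.

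**Conclusion.** No change to the plan follows. The missing definition is a gap that the plan's own text fills: censor at last contact, count adjudicated events through the Follow-Up Visit, and analyse once 250 are confirmed. The statisticians can record this at the blinded data review that Protocol 9.1 already schedules. The conflicting words on the trigger and the visit interval are clerical and do not alter the form of the primary test.

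Applied as written, the rule gives a sound randomized comparison. If there is no drug effect, the off-drug weeks add events at equal hazards in both arms and do not disturb the error rate. If there is an effect, the four-week window moves power from 80.5% to between 78.8% and 81.9%, within what approximately 80% conveys. Vital-status deaths move it by about one point at most. These figures assume constant hazards, uniform accrual, the plan's 5% yearly drop-out and a four-week window. The off-drug effect and the death rate after drop-out are assumptions, since the documents give neither, and the non-binding futility look is not modelled.

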8.3. Key Secondary Analysis

Similar to the primary analysis, the key secondary endpoints (listed in [section 3.2.2](#)) are also time-to-event variables and will be analyzed using time-to-event models and the stratified log rank test, as described for the primary analysis.

The key secondary analysis will be performed on FAS. The number and percentage of subjects experienced the broadly defined MACE, median survival time and corresponding 95% confidence intervals (CI) will be tabulated and presented by treatment group. A stratified log-rank test and corresponding test statistic, stratifying for country of enrollment and prescribed statin therapy (atorvastatin or rosuvastatin), at a two-sided alpha level of 0.05, will be used to compare the survival rate between the two treatment groups. For the purpose of all subsequent analyses listed below involving CV deaths, events within the “undetermined cause of death” category will be considered CV deaths.

No adjustment for multiplicity is needed for the primary hypothesis as there is no provision to terminate the trial for efficacy. A sequential gate-keeping approach will be used to control the overall Type I error rate when testing for the key secondary endpoints only if superiority is established for primary efficacy endpoint.

The key secondary endpoints will be tested sequentially following a pre-specified order as stated in [section 3.2.2](#) and re-emphasized below:

1. Time from randomization to the first occurrence of adjudication-confirmed MACE broadly defined between treatment groups.

2. Total incidence in narrow MACE (CV Death or Non-fatal MI or Stroke)
3. Time from randomization to CV Death or Non-fatal MI
4. Time from randomization to coronary heart disease (CHD) death or Non-fatal MI
5. Time from randomization to Non-fatal MI
6. Time from randomization to CV Death
7. Time from randomization to Stroke
8. All-cause mortality
9. Incidence of hospitalization for congestive heart failure (CHF)

The analysis of the key secondary endpoint will be repeated for the PPS set as the supportive analysis. Presentation of key secondary analyses will include estimated hazard ratios and associated 2-sided CI obtained from Cox Proportional Hazards (CPH) model with treatment as a factor, stratified by country of enrollment and prescribed statin therapy (atorvastatin or rosuvastatin).

Endpoints such as incidence of narrow MACE or incidence of CHF will allow consideration of recurrent events and will be evaluated using Andersen-Gill methodology in a proportional hazards model. Hazard ratios, confidence intervals, and p values will be presented as appropriate. Event rate and corresponding hazard ratios will be provided for all-cause mortality.

8.4. Other Secondary and Exploratory Analysis

Other secondary and exploratory endpoints are listed in [sections 3.2.2.1](#) and [3.2.3](#). Quantitative endpoints that are defined as a (percent) change from baseline will be analyzed using analysis of covariance (ANCOVA) models with treatment group, baseline value, and strata as covariates. Descriptive statistics for (percent) change from baseline at each post-baseline visit will be summarized using the FAS.

Descriptive statistics (number of subjects with non-missing values, mean, standard deviation, minimum, 25th percentile, median, 75th percentile, and maximum) will be used to summarize continuous variables by treatment group for the FAS set.

Least squares (LS) means and difference in LS means between RVX000222 and Placebo with standard errors (SEs) and 2-sided 95% CI and p-values obtained from ANCOVA model will be presented at each applicable post baseline visit.

Mixed-effects model repeated measures analysis will be used to model percent change in measurements over time at the last visit on treatment (LVT). An unstructured covariance matrix will be used to fit the underlying MMRM model. Subject and error will be considered random effects; all effects that include treatment, strata and baseline value will be considered fixed.

The pattern of change from baseline over time will also be displayed graphically in Figures for some endpoints. No multiplicity adjustment is planned to test the other secondary and exploratory endpoints. Since most of the other secondary endpoints are clinical laboratory tests, they are also summarized under safety analysis in [section 9](#).

Analyses will summarize EQ-5D-5L scale and subscale scores at each visit and change from baseline at each visit.

Analyses will address mean differences by treatment group on MOCA scale and differences for subjects with a baseline score indicative of cognitive impairment (Baseline MoCA < 26)

9. Safety Analysis

Safety data such as clinical laboratory results, vital signs, findings from physical examinations will be listed and/or summarized by treatment group where appropriate. No inferential hypothesis testing will be performed on the safety variables.

The assessment of safety will be based on the frequency, intensity, and types of AEs and for change and from Baseline in the clinical laboratory variables, and vital sign measurements.

